3.4.2 Tools Used for Data Collection

Subject Diary

Paper Diaries, hereafter referred to as Subject Diaries will be the only source document allowed for solicited local and systemic adverse events (including body temperature measurements), starting approximately 6 hours post-vaccination and collected by the subject. The following additional rules apply to documentation of safety information collected in the Subject Diary.

The Investigator or delegated staff should monitor the Subject's Diary status throughout the study for compliance and any solicited local and systemic adverse events that were of concern to the subject.

1. No corrections or additions to the information recorded by the subject within the Subject Diary will be allowed after it is delivered to the site.
2. Any blank or illegible fields on the Subject Diary must be described as missing in the CRF.

Case Report Forms

An electronic data capture (EDC) system (e.g., Inform™) will be used to expedite the entry of data. A qualified site staff member(s) will enter data in English into the web enable EDC system in a timely manner; the data will be stored in GSK clinical database management system. eCRF data will be reviewed routinely by GSK Data Management (DM) Group and GSK clinical monitors or representatives.

The information from the diary will be entered in the eCRF at visit 2. All data not recorded directly on the eCRFs must be verified by checking eCRF entries against source documents in order to ensure that the data have been completely and accurately reported as required by the study protocol.

Source data verification will be performed and recorded following GSK internal SOP. The subject must also allow access to his/her medical records. Each subject will be informed of this prior to the start of the study.

The following additional rules apply to documentation of Subject Diary information collected in the CRFs:

1. The site must enter all readable entries from the Subject Diary into the eCRF, including those values that may be biologically implausible (e.g. body temperature: 400°C).

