2. STUDY DESIGN

This is an open label, non-randomized, single center, Phase 1 clinical trial. The study includes a screening visit (performed at study Days -21 to -1), one clinical visit with vaccination (performed at study Day 1), 4 clinical visits (performed 7, 14, 28 and 84 days after vaccination), and 2 phone calls (performed 2 and 6 days after the vaccination).

Table 2-1 H03_01TP Study Design

| H03_01TP | H03_01E1TP | | | |
|---------------|---------------|-----------------------|--------------|---------------|
| | | | | |
| Vaccine group | No. subjects* | New enrolled subjects | No. subjects | Vaccine group |

| | | | |
|-------------------|----|----------------|------------------|
| 1790GAHB – 1 µg** | 5 | 5 | 1790GAHB – 25 µg |
| 1790GAHB – 5 µg | 4 | 4 | 1790GAHB – 25 µg |
| 1790GAHB – 25 µg | 2 | 2 | 1790GAHB – 25 µg |
| 1790GAHB – 50 µg | 4 | 4 | 1790GAHB – 25 µg |
| 1790GAHB – 100 µg | 5 | 5 | 1790GAHB – 25 µg |
| Placebo | 4 | 4 | 1790GAHB – 25 µg |
| Total H03_01TP | 24 | Naïve subjects | 26 |
| Grand total | | | 50 |

*only subjects with undetectable antibodies at baseline.

** µg of total protein

Up to 50 subjects will be enrolled into this trial. Up to 24 subjects are eligible from the parent H03_01TP trial. With respect to naïve subjects who were not part of H03_01TP study, considering that in the original H03_01TP population 50% of subjects did not have detectable antibodies at baseline, with 26 subjects, approximately 13 subjects should not have detectable antibodies. This number combined with that of placebo recipients in H03_01TP should be sufficient to allow a balanced contribution of previously unvaccinated and vaccinated subjects in the extension trial.

Blood Draw Procedure

A blood draw will be obtained for hematological and serological (HIV, hepatitis B and C) tests for subjects who were part of the parent trial (H03_01TP). For naïve subjects a blood draw will be obtained for the same hematological and serological tests mentioned above and in addition for HLA-B27 testing as part of the initial screening.

One additional blood draw for hematological tests will be obtained at 7 days (Visit 2) and 84 days (Visit 5) after vaccination.

Each subject will have blood drawn for immunological studies before and 7, 14, 28 and 84 days after vaccination. For the purpose of creating a standard reference serum for the serological assay, an additional blood sample will be collected at 28 days after vaccination (Visit 4).

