For each of the time points or time intervals presented in the summaries, only subjects with at least one plausible observation (i.e., any non-missing values but excluding “Not done/unknown” and implausible values) for the solicited adverse events will be considered. Subjects without plausible data (i.e. missing values or reported as “Not done/unknown” and implausible values) will be removed from the denominator to prevent a downward bias (towards zero). Level 1: Daily reports of solicited adverse event

For each of the time points only subjects with at least one plausible observation (i.e., any non-missing values but excluding “Not done/unknown” and implausible values) for the solicited adverse event in the interval of interest will be considered. Subjects without plausible data (i.e. missing values or reported as “Not done/unknown” and implausible values) will be removed from the denominator in order to prevent a downward bias (towards zero). Data collected will be summarized (frequencies and percentages of subjects) by vaccine group, solicited adverse event and time point.

Level 2: Time of first onset of solicited adverse events

The time of first onset is defined, for each subject, for each solicited adverse event, as the time point at which the respective solicited adverse event first occurred. For erythema, induration the following threshold(s) will be used ≥ 25 mm. The summary will provide the frequencies and percentages of subjects with first onset of each solicited adverse events by vaccine group and by each time point.

Level 3: Solicited adverse events, maximum event severity by event and interval

The **maximum event severity** will be defined if there is at least one plausible nonmissing observation (excluding “Not done/unknown” and implausible values) within this time interval, Each subject’s data will be aggregated across the time points of the interval and summarized according to the maximal severity observed for each adverse event, followed by a summary across subjects for each vaccine. Subjects without any solicited adverse

events in the interval, i.e., missing values at each of the requested time points, will be removed from the denominator.

Level 4: Solicited adverse events, occurrence of at least one event by category (local, systemic) and interval.

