7. ANALYSIS INTERPRETATION

All analyses will be descriptive.

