12. ANNEX 2: SUMMARY ON ELIMINATION CODES

Table 12-1 Safety Sets

| PD code | PD Description | Study Period | All Exposed Set | Overall Safety Set | Safety Set, Unsolicited AEs, All study period | Safety Set, Solicited AEs, Period T30-D7 |
|----------------|---|---------------------|------------------------|---------------------------|--|---|
| | Exclusion code | | EXPFL | SAFL | SSU10FL | SSS10FL |
| 100 | Study vaccine not administered AT ALL | All Study | EXC | EXC | EXC | EXC |
| 115 | Subject did not provide any post-vaccination unsolicited safety data | All Study | | | EXC | |
| 116 | Subject did not provide any post-vaccination solicited safety data | All Study | | | | EXC |

EXC = excluded from this analysis set.

Table 12-2 Immunogenicity Sets

| PD code | PD Description | Study Objective/Period | All Exposed | FAS (Overall) |
|----------------|--|-------------------------------|--------------------|----------------------|
| | Exclusion code | | EXPFL | FAS_0 |
| 100 | Study vaccine not administered AT ALL | All Study | EXC | EXC |
| 110 | Serological results are not available (all time points) | All Study | | EXC |

FAS = Full Analysis Set;

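### At Levels 3 and 4 the solicited-event denominator rule only partly prevents the downward bias it names, because clinic readings keep subjects with no diary, or a short one, in the table as event-free

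*SAP*

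**What the plan says.** SAP 6.5.2.2 (Solicited Adverse Events) defines four levels of summary. At every time point or interval, "only subjects with at least one plausible observation" count, and subjects without plausible data "will be removed from the denominator to prevent a downward bias (towards zero".

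The interval rules are these:
- **Interval.** Levels 3 and 4 use a single interval, from 30 minutes after vaccination to Day 7. SAP Annex 2, Table 12-1, labels the solicited safety set with the same period.
- **Level 3.** Maximum severity "will be defined if there is at least one plausible nonmissing observation" in the interval, and subjects are "summarized according to the maximal severity observed for each adverse event". Removal requires missing values at every time point.
- **Level 4.** A subject with any report above *none* is *any*. Every other subject in the denominator is *none*.
- **Safety set.** Code 116 in Annex 2 excludes a subject only if "Subject did not provide any post-vaccination solicited safety data".

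The protocol supplies the rest. Note e to Table 2 schedules clinic assessments at about 30 minutes and 4 hours after vaccination. Section 3.4.2 starts the diary at about 6 hours and adds: "Any blank or illegible fields on the Subject Diary must be described as missing in the CRF". Section 8.4.2.1.2 summarises days 1-3, 4-7 and 1-7 without the 30-minute and 4-hour readings, which get their own summary. SAP 6.5.1 refers the reader to that protocol section, yet 6.5.2.2 merges the clinic readings into the interval, and SAP section 9 gives changes from planned analyses as not applicable.

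**The concern.** The SAP names a bias and adopts a rule against it, but its choice of interval lets part of that bias back in. Almost every vaccinated subject will have a clinic reading before the first diary entry. A subject who was well at 30 minutes and 4 hours and never hands in a diary therefore meets the one-reading test and enters the week's table as *none*. The same holds for a diary abandoned before the first reaction. Code 116 would rarely apply.

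Events lost this way do not return to the solicited tables. Under protocol 3.4.2 nothing may be added to the diary after delivery, and a solicited event first reported verbally is entered as an unsolicited one.

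Solicited reactions within 7 days are a secondary safety endpoint, and SAP 6.5.2 shows boosted (Shigella) and first-dose (Pla+Naïve) subjects in the same tables. Incomplete diaries would lower the rates. If completion differed between the groups, part of any visible difference in reactogenicity would come from missing data.

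**Working it through.** The plan states no event rate, diary-return rate or bias figure, so there is nothing of its own to reproduce.

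**Inputs from the documents.** Planned size: "Up to 50 subjects will be enrolled into this trial". SAP Table 2-1 gives 5 + 4 + 2 + 4 + 5 = 20 previously vaccinated, 4 placebo and 26 naïve subjects, so Shigella 20 and Pla+Naïve 4 + 26 = 30.

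**Assumed inputs.** True share with the event p = 50%. Share with clinic readings but no diary q = 5%, 10% or 20%. Share of events visible only in the diary s = 80% (range 50% to 100%). Chance that a given diary day is missing m = 5%, 10% or 20%. Event duration d = 1, 2 or 3 days. Missingness is taken as unrelated to events.

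**Step 1. The bias the rule removes.** If subjects with no data at all were kept as *none*, the rate would be p(1 − q) = 47.5%, 45.0% or 40.0%. Removing them gives 50%. For these subjects the rule works.

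**Step 2. The bias left by clinic readings.** When everyone with a clinic reading is kept, the reported rate is p(1 − qs):

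| No diary (q) | Calculation | Reported |
|---|---|---|
| 5% | 0.50 × (1 − 0.05 × 0.8) | 48% |
| 10% | 0.50 × (1 − 0.10 × 0.8) | 46% |
| 20% | 0.50 × (1 − 0.20 × 0.8) | 42% |

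The relative loss is qs. It runs from 0.05 × 0.5 = 2.5% to 0.20 × 1.0 = 20% over the assumed ranges. A simulation at q = 10%, s = 80% gave 46.1%.

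**Step 3. In subjects.** Events missed = n × q × p × s. At q = 10% this is 20 × 0.10 × 0.5 × 0.8 = 0.8 (Shigella), 30 × 0.04 = 1.2 (Pla+Naïve) and 50 × 0.04 = 2.0 overall. If 20% of one group and none of the other returned no diary, a gap of 50 − 42 = 8 points would appear without any true difference. In the group of 20 that is 20 × 0.20 × 0.5 × 0.8 = 1.6 subjects.

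**Step 4. Scattered missing days.** With seven diary days and at least one reading, the reported rate is p(1 − m^d)/(1 − m^7):

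| m | 1-day event | 2-day event | 3-day event |
|---|---|---|---|
| 5% | 47.5% | 49.9% | above 49.9% |
| 10% | 45.0% | 49.5% | 49.95% |
| 20% | 40.0% | 48.0% | 49.6% |

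The loss is small once an event lasts 2 days or more.

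**Step 5. Diaries stopped for good.** The loss has the same form as step 2, with q the share who stop and s the share of events that first occur after the stop. The documents give no onset distribution, so no figure is put on it.

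**Step 6. The protocol's intervals.** With the clinic readings left out, a non-returner has no observation in days 1-7, so the SAP's own rule removes that subject. A subject who stops on Day 2 leaves the day 4-7 denominator but stays in day 1-7.

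**The case against.** The strongest case against the point is that the quoted sentence is correct for what it covers. It concerns subjects without plausible data, removes them, and works at Level 1 time points. A reader might infer that the rule fails altogether, or that the SAP imputes blank days as *none*. The documents support neither. The CRF records a blank as missing, Level 3 takes the maximum of what was observed, and a subject with any observed event still counts as *any*. The *none* for a partly observed week follows from the Level 3 and Level 4 definitions and is not a stated imputation.

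The protocol also works against diary loss. Reminders go out on days 3 and 7 (5.2.2), the diary is collected with an interview at Visit 2 (5.3.1), and a subject who does not hand it in must be telephoned (3.8). Events told verbally reach the combined solicited and unsolicited summary (SAP 6.5.2.4). Level 1 denominators, if read per time point, would expose uneven loss. Finally, "All analyses will be descriptive", so no test is affected.

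These points stand, and they limit the size and consequence of the problem. They do not remove it. Chasing diaries reduces non-return without ensuring that every diary comes back, the combined summary does not correct Levels 3 and 4, and the departure from the protocol's separate summaries remains undeclared.

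**Conclusion.** The point holds as a minor one. At Levels 3 and 4 the rule prevents the named bias incompletely: subjects with no diary or a short one can appear as *none* through Day 7 because clinic readings qualify them. The documentable cause is the SAP's merging of clinic and diary readings, which the protocol keeps apart, with no change recorded in section 9.

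The size is unknown. The fall from 50% to 48%, 46% or 42% rests entirely on assumed event, visibility and non-return rates, and on missingness unrelated to reactions. If reactions influence diary return, the error could be larger, smaller or in the other direction. A reader might take the 8-point gap in step 3 as an expected artefact. It is not: nothing in the documents suggests that 20% of one group would fail to return diaries.

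**What to change.** In SAP 6.5.2.2, restore the protocol's separation:

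- Summarise the 30-minute and 4-hour readings in their own table. Requiring a diary reading without this table would drop a subject who reacted in clinic and returned no diary.
- Compute Levels 3 and 4 on the diary period (days 1-3, 4-7 and 1-7) and require at least one diary reading in the interval to enter the denominator.
- Show by group the number of subjects with no diary and with an incomplete diary.
- Repeat Levels 3 and 4 in subjects with readings on all seven diary days. Label this a sensitivity table, since completers are a selected group. It is needed because the one-reading requirement does not deal with diaries that stop early.
- In the Level 3 removal sentence, refer to subjects without solicited *data*. Taken literally, its opening words would remove event-free subjects and bias rates upward.

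In the step 2 illustration with q = 10%, removing non-returners brings the diary-period rate back from 46% to 50%, provided that events seen in clinic are also entered in the diary.

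If the sponsor prefers to keep the merged interval, section 9 should record it as a change from the protocol, and the completeness counts and sensitivity table should still be produced.

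Cost: one sentence in the SAP, one or two extra tables from data already collected, and slightly smaller denominators.

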6.5.2.3. Unsolicited Adverse Events

All the unsolicited adverse events occurring during the study, judged either as probably related, possibly related, or not related to vaccination by the investigator, will be recorded. The original verbatim terms used by investigators to identify adverse events in the CRFs will be mapped to preferred terms using the MedDRA dictionary. The unsolicited adverse events will then be grouped by MedDRA preferred terms into frequency tables according to system organ class. Adverse events judged by the investigator as at least possibly related to study vaccine will be summarized by vaccine group, according to system organ class and preferred term within system organ class. When an unsolicited adverse event occurs more than once for a subject, the maximal severity and strongest relationship to the vaccine group will be counted.

Only vaccine-emergent adverse events (see **section 7.1** of protocol for definition) will be analyzed, i.e., excluding those after a subject has given informed consent but before vaccination.

The summaries will be presented for all study period and will include frequency distributions of the different adverse events:

- Onset between day 1 and study termination (all study period).

The analysis of unsolicited adverse events comprises the following categories:

- Any unsolicited adverse event.
- Possibly or probably related unsolicited adverse events.
- Unsolicited adverse events leading to death.
- Serious adverse events.
- Possibly or probably related serious adverse event.
- Unsolicited adverse events leading to premature withdrawal from study.
- Unsolicited adverse events leading to hospitalization.
- Unsolicited adverse events of special interest.

- Solicited adverse events continuing beyond day 7 will be coded by MedDRA and combined with the respective unsolicited adverse events.

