		1	3, 7 V1+2 days; V1+6 days	8 V1+7 days	15 V1+14 days	29 V1+28 days	85 V1+84 days	
		Visit Window (Days)	-21 to -1	n/a	n/a	0 to +1	0 to +4	-3 to +7
Visit Number		Screening	1		2	3	4	5
Study Event	References							
Study Treatment								
Vaccination	Section 5.2		X					
Screening and Safety								
Informed Consent ^a	Section 5.1.1	X						
Medical History	Sections 5.1.2	X						
Physical Exam ^b	Sections 5.1.2 and 5.1.3	X	X					
Symptom-directed physical Exam ^b	Section 5.3.1				X	X	X	X

Vital signs (temperature, respiratory rate, heart rate, blood systolic and diastolic pressure)	Sections 5.1.2 Screening and 5.2.1 Post-vaccination Procedures	X	X					
Safety blood draw (Hematology)	Sections 3.5 and 7.1.7	X			X			X

Visit Type Study Day Visit Window (Days) Visit Number	Clinic Visit	Clinic Visit	Phone Call	Clinic Visit	Clinic Visit	Clinic Visit	Clinic Visit	Clinic Visit	
		1	3, 7 V1+2 days; V1+6 days	8 V1+7 days	15 V1+14 days	29 V1+28 days		85 V1+84 days	
	-21 to -1	n/a	n/a	0 to +1	0 to +4	-3 to +4		-3 to +7	
	Screening	1		2	3	4		5	
Study Event	References								
Serology (HIV, hepatitis B and C, and HLA-B27 testing only for naïve subjects) ^d	Section 3.5 and 5.1.2	X							
Pregnancy Test	Sections 3.5 and 5.1.2		X					X	
Exclusion/Inclusion Criteria	Section 4	X							
Post Injection Assessment ^e	Section 5.2.1		X						
Subject Diary Dispensed with Training	Section 5.2.1		X						

Subject Diary Reminder Call	Section 5.2.2			X				
Subject Diary Reviewed and Collected	Section 5.3.1				X			
Assess all AEs	Section 7.1	X	X		X	X	X	
Assess SAEs	Section 7.1.4	X	X		X	X	X	X
Assess for NOCDs, medically attended AEs, AEs leading to withdrawal, and AESIs	Sections 7.1.4.1 and 7.1.3		X		X	X	X	X

Number	Study Event	Visit Type	Clinic Visit	Clinic Visit	Phone Call	Clinic Visit	Clinic Visit	Clinic Visit
		Study Day		1	3, 7 V1+2 days; V1+6 days	8 V1+7 days	15 V1+14 days	29 V1+28 days
		Visit (Days)	-21 to -1	n/a	n/a	0 to +1	0 to +4	-3 to +4
		Window	Screening	1		2	3	4
Visit	References							
Assess relevant medications	Sections 5.1.2 and 6.5	X	X		X	X	X	X
Immunogenicity								
Serology blood draw	Section 3.5		X		X	X	X	X

Additional blood draw for preparation of standard serum	Section 3.5						X	
Study Completion Procedures								
Study Termination ^f	Section 5.5							X

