- Potential immune-mediated diseases (pIMDs): a subset of AEs that include autoimmune diseases and other inflammatory and/or neurologic disorders of interest which may or may not have an autoimmune aetiology. In this study, only the pIMDs reported in the table below will be collected. However if other pIMDs are discovered during development of the vaccine, the table will be revised and updated accordingly.

Musculoskeletal disorders	Spondyloarthritis, including ankylosing spondylitis, reactive arthritis (Reiter's Syndrome) and undifferentiated spondyloarthritis
Blood disorders	Autoimmune neutropenia

If solicited or unsolicited adverse events have been reported and the subject indicated that the symptoms required medical attendance or were of concern, the subject must be contacted for further information.

When the subject is contacted for any of these reasons, the contact must be documented in the subject's source documentation.

All AEs, regardless of severity, will be monitored until resolution or until the investigator assesses them as chronic or stable. All subjects experiencing AEs - whether considered associated with the use of the study vaccine or not - must be monitored until symptoms subside and any abnormal laboratory values have returned to baseline, or until there is a satisfactory explanation for the changes observed, or until death, in which case a full pathologist's report should be supplied, if possible. The investigator's assessment of ongoing Adverse Events at the time of each subject's last visit should be documented in the subject's medical chart.

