8.4.2.1.3 Analysis of Unsolicited Adverse Events

This analysis applies to all adverse events occurring during the study, judged either as probably related, possibly related, or not related to vaccination by the investigator, recorded in AE CRF, with a start date on or after the date of vaccination. AE starting prior to the vaccination will only be listed. The original verbatim terms used by investigators to identify adverse events in the CRFs will be mapped to preferred terms using the MedDRA dictionary. The adverse events will then be grouped by MedDRA preferred terms into frequency tables according to system organ class.

All reported adverse events, as well as adverse events judged by the investigator as at least possibly related to study vaccine, will be summarized according to system organ class and preferred term within system organ class. These summaries will be presented by vaccination group and by interval of study observation. When an adverse event occurs more than once for a subject, the maximal severity and strongest relationship to the vaccine group will be counted.

Separate summaries will be produced for the following categories:

- Serious adverse events
- Adverse events that are possibly or probably related to vaccine

- Adverse events of special interest
- New onset of chronic disease
- Potential immune-mediated diseases (pIMDs) adverse event leading to withdrawal • Adverse events leading to a medically attended visit
- Adverse event by data source.

Data listings of all adverse events will be provided by subject. In addition, adverse events in the categories above will be provided as listed data.

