8.5 Sample Size and Power Considerations of Primary and Secondary Objectives

No formal statistical sample size and power computations are performed since the objectives of the study are to descriptively assess the immunogenicity and safety of the investigational vaccine.

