9. CHANGES FROM PLANNED ANALYSES

Not Applicable.

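### SAP 6.5.2.3 omits four adverse-event summaries that protocol V2 8.4.2.1.3 requires, and SAP section 9 declares no change; counts of subjects with medically attended AEs and new-onset chronic disease have no substitute

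*SAP*

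**What the plan says.** Protocol V2 section 8.4.2.1.3 states "Separate summaries will be produced for the following categories" and names serious AEs, vaccine-related AEs, AESIs, "New onset of chronic disease", pIMDs, AEs leading to withdrawal, "Adverse events leading to a medically attended visit" and AEs by data source. It asks for listings of the same categories as well.

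The protocol also plans the collection behind these classes. Table 2 has a row "Assess for NOCDs, medically attended AEs, AEs leading to withdrawal, and AESIs", marked at Visits 1 to 5. Section 5.5 repeats medically attended AEs and NOCD in the Day 85 interview. Section 7.1.3 has the investigator evaluate each AE for medical attendance, NOCD, withdrawal and pIMD status. For pIMDs it adds "In this study, only the pIMDs reported in the table below will be collected", with a short table of terms.

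SAP 6.5.2.3 opens its list with "The analysis of unsolicited adverse events comprises the following categories". The items are any unsolicited AE, related AEs, deaths, SAEs, related SAEs, withdrawals, hospitalizations and AESIs, plus a rule that solicited events lasting beyond day 7 are pooled with unsolicited ones. SAP section 9, on changes from planned analyses, reads "Not Applicable".

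**The concern.** The SAP was written against protocol V2 (SAP section 1), so a version difference does not explain the shorter list. A programmer who works from the SAP as written would not produce four outputs that the protocol promises, and a reader of section 9 would believe that nothing had changed.

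The omitted safety classes are ones the site is told to ask about. General AE collection stops at Visit 4 (protocol 7.1). After that, the non-serious events still sought are those that are medically attended, clinically significant in the investigator's view, AESIs, NOCD or linked to withdrawal (7.1, 5.5). If the late follow-up is worth collecting by class, it should be possible to read from the tables how many subjects in each group had such an event.

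**Working it through.** There is no planned figure to reproduce. The study is descriptive, and protocol 8.5 says "No formal statistical sample size and power computations are performed". The check is a comparison of the two lists.

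| Protocol V2 8.4.2.1.3 | SAP 6.5.2.3 |
|---|---|
| Serious AEs | Kept |
| Possibly or probably related AEs | Kept |
| AESIs | Kept |
| AEs leading to withdrawal | Kept |
| NOCD | Absent |
| pIMDs | Absent |
| Medically attended AEs | Absent (hospitalization only) |
| AEs by data source | Absent |

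**Count.** 8 required, 4 kept, 8 − 4 = 4 absent. In the protocol text the pIMD and withdrawal items run together in one bullet. I read them as two, because 7.1.3 defines them separately. Read as one bullet there are 7 items: three are wholly absent, and the pIMD part of the combined bullet is still unmatched.

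**Elsewhere in the SAP.** Medically attended AEs, NOCD and pIMDs appear nowhere else, including the abbreviation list. The safety pointer in SAP 6.5.1 goes to protocol 8.4.2.1.2, which covers solicited events, and not to 8.4.2.1.3. Annex 3 says only that standard mock tables will be used.

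**Do the kept categories substitute?**

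- *Medically attended AEs.* Protocol 7.1.2 and 7.1.3 include any visit to a healthcare provider. Hospitalization is a subset.
- *NOCD.* No item in the SAP list corresponds.
- *pIMDs.* The 7.1.3 table lists spondyloarthritis (ankylosing, reactive and undifferentiated) and autoimmune neutropenia. The AESIs in 7.1.4.1 are reactive arthritis and neutropenia. The remainder is mainly ankylosing and undifferentiated spondyloarthritis. Section 7.1.4.1 also ties AESI neutropenia to the 7-day time point, so a later autoimmune neutropenia could fall outside it if that wording is applied literally.

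**What remains visible.** The any-unsolicited-AE tables run from day 1 to study termination, by system organ class and preferred term. SAP 6.5.2 shows safety tables for Shigella, Pla+Naïve and Total. From Table 1 the maximum group sizes are 5 + 4 + 2 + 4 + 5 = 20, 4 + 26 = 30, and 50. Each event therefore has a preferred-term row with a count per group. Those rows do not show whether an event was medically attended. They also cannot be added into a number of subjects, because one subject may appear in several rows.

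**Period concerned.** On nominal visit days, restricted collection runs from 28 to 84 days after vaccination: (84 − 28)/84 = 56/84 = 67% of follow-up time. This is a share of time and does not measure information lost.

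**The case against.** The strongest defence is that SAP 6.5.2.3 sits under a heading for additional considerations, so its list may add to the protocol's plan without replacing it; section 9 would then be accurate. The table inventory is in a TFL table of contents (SAP section 10) that was not supplied and may contain these outputs, and nothing in the SAP revokes the protocol's listings. This limits what can be claimed, but it does not reconcile the texts. The SAP list is worded as what the analysis consists of, and the only pointer back to the protocol's safety analysis leads to the solicited-event section.

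A reader might infer that safety signals would go unreported. The documents do not support that. Every such event recorded as an AE counts in the any-unsolicited-AE tables, and a single new spondyloarthritis would have its own row by group. Nor are the final tables the only route: protocol 7.1.5 requires follow-up information on SAEs and pIMDs to reach the sponsor within 24 hours, and 7.1.2 tells subjects to report medically attended events promptly.

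A reader might also infer that the AESI table misses the pIMDs as a class. It does not. Reactive arthritis and neutropenia are covered, and haematology shift tables by group (SAP 6.5.2.5) give further sight of neutrophil counts. Protocol 5.4 speaks of neutropenia at any time in the study, so the 7-day wording may not be meant as a limit. The remaining conditions concern at most 50 adults, with HLA-B27 positivity and a history of reactive arthritis excluded (4.2).

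Finally, none of the four omitted summaries is a named secondary safety endpoint, and the data-source table concerns provenance and is not a class of safety event. Both points stand.

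**Conclusion.** The omission is real and undeclared. Four of eight required summaries are missing from the SAP list (with the run-together bullet read as two), and section 9 is wrong as it stands. The practical loss is narrower than that count suggests. It consists of the per-group number of subjects with any medically attended AE and with any NOCD, plus a small residual part of the pIMD class. The events themselves and all named endpoints remain reportable. Explicit collection to Visit 5 applies to medically attended AEs and NOCD; for pIMDs it follows only through their overlap with AESIs.

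The conclusion rests on the SAP text. If the unseen TFL table of contents includes these tables, the outputs may exist, but the SAP still needs to agree with the protocol. This is a correction that should be made, and it does not threaten the trial's conclusions.

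**What to change.** 1. Add to the SAP 6.5.2.3 list, for Shigella, Pla+Naïve and Total: unsolicited AEs leading to a medically attended visit, NOCD, and pIMDs using the terms tabulated in protocol 7.1.3. Give each a count of subjects and a subject listing.
2. Extend the pointer in SAP 6.5.1 to include protocol 8.4.2.1.3.
3. Restore the summary by data source, or declare and justify its removal in SAP section 9. The same applies to any other category the sponsor decides to leave out.

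The cost is a small SAP revision and three or four short tables with listings. No further data collection is needed, provided the classifications that investigators make under 7.1.3 are captured on the CRF. The CRF is not among the documents, so this should be confirmed first.
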